### **3 INTERIM MONITORING EXAMPLE TO ILLUSTRATE PROVISION OF DOSE RECOMMENDATIONS DURING DOSE ESCALATION IN MONOTHERAPY**

In order to provide a comprehensive view of the dynamics of the models, different hypothetical scenarios exploring all possibilities are examined. For the simplicity of illustration purposes, a static cohort size of 3 subjects is applied for dose levels  $3 \times 10^{10}$ ,  $3 \times 10^{11}$ ,  $1 \times 10^{12}$ , and  $3 \times 10^{12}$  vp in the BMS-986277 monotherapy. This cohort size could vary during the actual clinical trial, and the BLRM models are designed to fit various different cohort sizes, adaptively. In general, there are 4 possible scenarios for a specific dose level; these are 0 DLT observed in 3 total subjects in that cohort (denoted as 0/3), 1 DLT observed in 3 subjects (1/3), 2 DLTs observed in 3 subjects (2/3), and 3 DLTs observed in 3 subjects (3/3).

[figure not shown]
During interim monitoring, posterior probabilities will be updated when there is new DLT information available. The following 3 visualization plots will be produced to reflect the real-time dose-DLT relationship, to quantify benefit (in the form of target dosing) and risk (in the form of overdosing and underdosing) during model's recommendation process, and to facilitate clinical team's interpretation of the model recommendations for decision making:

- Dose-DLT profile for the doses ranging between 0 and  $3 \times 10^{12}$  vp (Figure 1).
- Stacking histograms displaying predictive probabilities on DLT rates classified into 3 different categories (Underdosing, Target dosing and Overdosing) (Figure 2).
- Box plots summarizing the Markov Chain Monte Carlo samples of predicted DLT rates for the 4 prespecified dose levels (Figure 3).

In the following illustrations, Figure 1 to Figure 3 are produced using a hypothetical example assuming 0/3 DLTs observed in the  $3 \times 10^{10}$  vp cohort and 1/3 DLTs observed in the  $3 \times 10^{11}$  vp cohort.

**Figure 1: Updated Dose-DLT Profile After Incorporating Prior Information and All Previous and Current DLT Information**

Abbreviations: L = lower DLT boundary; U = upper DLT boundary.

**Interpretation and Use of Figure 1:**

Figure 1 is a snapshot of an updated dose-DLT profile with DLT information available at dose level  $3 \times 10^{10}$  vp for monotherapy. The dose-DLT profile is captured with a continuous dose spectrum ranging from 0 to  $3 \times 10^{12}$  vp. For each dose within the range, there is a corresponding distribution of the predicted DLT rates calculated from the posterior samples of the model parameters. This figure will be updated each time new DLT information becomes available from the study.

[figure not shown]
In Figure 1, there are 3 different quantiles (2.5%, 50%, and 97.5%) plotted to characterize the current trend of the toxicity profile (as shown by the 50% quantile), as well as the variation of the dose-DLT profile (as shown by the 2.5% percentile and the 97.5% percentile), according to the accumulation of DLT data from all previous and current dose levels. The toxicity boundaries (low

boundary 0.16 and high boundary 0.33) are illustrated in two dotted horizontal lines to benchmark the way in which the dose-DLT profile is trending.

Intermediate dose levels can be identified using different boundary cutoffs. For example, using the 50% percentile curve (green highlight), which represents the nearly average DLT distribution for each dose level, the  $7 \times 10^{11}$  vp could be a potential intermediate dose level corresponding to the lower prespecified DLT rate boundary of 0.16, and the  $2.4 \times 10^{12}$  vp dose could be a fitted MTD dose level associated with the upper boundary of 0.33.

Moreover, if all of the current pre-specified doses are considered intolerable (overdosing probabilities > 0.35 for monotherapy, a case not shown on the current Figure 1), the model will recommend to stop the current dose level, and the clinical team can leverage the current updated dose-DLT curve to pinpoint a new dose, which is lower than pre-specified lowest dose ( $3 \times 10^{10}$  vp) by using the DLT-rate boundaries.

**Figure 2: Updated Stacking Histogram After Incorporating Prior Information and All Previous and Current DLT Information to Classify Predicted DLT Rates into 3 Categories (Underdosing, Target Dosing, and Overdosing)**

### Interpretation and Use of [Figure 2](#):

[figure not shown]
Figure 2 is a snapshot of stacking histogram with DLT information available at dose level  $3 \times 10^{10}$  vp and  $3 \times 10^{11}$  vp. This figure will be updated each time new DLT information becomes available.

When recommending the next dose level, the model will first exclude doses that are intolerable (with overdosing probabilities > 35%, the rate that has been specified for BMS-986277). Among those qualified candidate doses that are considered “tolerable”, the model will select the dose that maximizes the probability of being within the target toxicity range (DLT rate between 16% and 33%). However, there will be no dose skipping during the dose escalation monotherapy phase of the study.

As illustrated in Figure 2, the distribution of predicted DLT rates will be characterized into possibilities falling into 3 different categories. First, dose levels  $3 \times 10^{12}$  vp for BMS-986277 are excluded according to the higher-than-cutoff overdosing probabilities (0.579 for  $3 \times 10^{12}$  vp). Among the remainder of tolerable dose levels, the BLRM recommends the dose that maximizes the probability of being within the target dosing interval. Therefore, the model’s recommendation would be to stay at  $1 \times 10^{12}$  vp, which is associated with the highest target dosing probability of 0.418 compared with that of  $3 \times 10^{10}$  vp (0.068) and  $3 \times 10^{11}$  vp (0.254).

Similarly (although not shown on Figure 2), according to the rules specified above, the model could possibly recommend to de-escalate to a lower dose level than the current treated dose level, escalate to the next dose level, or even recommend to stop and identify a new dose level lower than  $3 \times 10^{10}$  vp, the lowest pre-specified dose level. Please refer to the description of [Figure 1](#) for details on how to specify the new dose levels.

**Figure 3: Updated Box Plot After Incorporating Prior Information and All Previous and Current DLT Information**

**Interpretation and Use of Figure 3:**

Figure 3 is a snapshot with DLT information available at dose level  $3 \times 10^{10}$  vp and  $3 \times 10^{11}$  vp. The dose-DLT distributions calculated from the posterior samples of the model parameters are characterized in the format of boxplots for the pre-specified dose levels. This figure will be updated each time there is new DLT information available.

This plot supplements the information provided in Figure 1. It allows for a more in-depth and focused visualization of general trend of dose-DLT relationship, as well as the magnitude and variability in the DLT rates for each pre-specified dose level.

The illustration in this section is for the monotherapy dose escalation, but the same concepts can be applied to BMS-986277 in combination with nivolumab.

**3.1 Example of using the BLRM for BMS-986277 Monotherapy Dose Escalation**

[figure not shown]
According to safety consideration and clinical judgement, the dose level  $3 \times 10^{10}$  vp is recommended as the starting dose for BMS-986277 monotherapy. With the current BMS-986277 prior specified in the Section 1.2 and all available DLT information up to  $3 \times 10^{12}$  vp, a

corresponding decision tree illustrating various models' recommendations under all possible scenarios for the first two cohorts is provided in Figure 4.

Tracing a branch of the decision tree in Figure 4 illustrates the decision making process. Taking the left-most branch of the tree as an example, starting at  $3 \times 10^{10}$  vp, if there were 0 DLTs observed in the real clinical trial, the model would recommend to escalate to  $3 \times 10^{11}$  vp (the BLRM actually recommends escalating to the highest dose  $3 \times 10^{12}$  vp, but since this is a 100-fold increase of dose and dose skipping is not allowed, the dose level  $3 \times 10^{11}$  vp is selected), one level above the current treated dose level according to the escalation rules per protocol. Next, if there is 0 DLTs observed at  $3 \times 10^{11}$  vp, the model would recommend to escalate further to  $1 \times 10^{12}$  vp. At  $1 \times 10^{12}$  vp, there would be 3 potential decisions (0/3 escalate, 1/3 and 2/3 would stay, and 3/3 would de-escalate); this is not shown due to crowding the diagram.

During the actual clinical study, the tree would be narrowed or deepened based on actual DLTs observed. The clinical team will be able to leverage this decision tree to preview decisions at each interim monitoring step and to plan proactively.

**Figure 4: The BLRM Model Hypothetical Decision Tree for BMS-986277 Monotherapy during Dose Escalation (for the first 2 cohorts)**

Abbreviations: DE = de-escalation; E = escalation; S = stay.

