##### 1.2 Prior Specification for BMS-986277 Monotherapy

The Bayesian approach requires the specification of prior distributions for model parameters, which include parameters  $(\alpha_1, \beta_1)$  for BMS-986277. A mixture prior will be used for parameters  $(\alpha_1, \beta_1)$  for BMS-986277. There are two bivariate normal components in generating this mixture prior:

- Meta-analytic predictive (MAP) component: Obtained based on the clinical safety and exposure profiles of enadenotucirev using the MAP approach, because BMS-986277 is the genetically modified form of enadenotucirev.
- Weakly informative prior for BMS-986277 component: Reflecting the potential higher toxicity of BMS-986277 than enadenotucirev from activating T-cells and allowing for considerable prior uncertainty.

Derivation of prior distribution of these parameters is provided in the following subsections.

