### 1.2.2 Weakly Informative Prior for BMS-986277 Component

- The median toxicity rate at the BMS-986277 reference dose (3x10^12) was assumed to be 30%, ie, mean ( $\log(\alpha_1)$ ) =  $\text{logit}(0.30) = -0.847$ .
- A doubling in dose was assumed to double the odds of DLT, ie, mean( $\log(\beta_1)$ ) = 0.
- The standard deviation of  $\log(\alpha_1)$  was set to 1.53 using the following steps:
  - If the toxicity probability range was set to be [1%, 99%], then the toxicity interval would be  $\text{logit}(0.99) - \text{logit}(0.01) = 9.19$ .
  - To cover 99.7% of the variance, the toxicity interval will cover  $6 \cdot \text{sd}(\log(\alpha_1))$ , which results in  $\text{sd}(\log(\alpha_1)) = 9.19/6 = 1.53$ .
- The standard deviation of  $\log(\beta_1)$  was set to 2, which allows for considerably large prior uncertainty for the dose toxicity relationship.

- The correlation between  $\log(\alpha_1)$  and  $\log(\beta_1)$  was assumed to follow a uniform(-1, 1) distribution with mean 0 (assuming independence of  $\log(\alpha_1)$  and  $\log(\beta_1)$ ).
- $\log(\alpha_1)$  and  $\log(\beta_1)$  follow a bivariate normal distribution.

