### 1.2.3 Mixture Prior

To obtain the mixture prior, 50% weight is assigned to the MAP component (described in Section 1.2.1), and 50% weight is assigned to the weakly informative component (described in Section 1.2.2) to balance the previous experience with enadenotucirev and potential unknown toxicity profile of BMS-986277.

The mixture prior will be fitted into EAST® v6.3.1 Dose Escalation Module by Cytel for the Monotherapy Escalation (Part 1A) as stated in model setup section.

The mixture prior with both MAP and weakly informative components for the BLRM parameters of BMS-986277 is generated using R v3.4.1 and R2OpenBUGS package v3.2 and summarized in Table 2.

**Table 2** Prior Distribution for Model Parameters ( $\log(\alpha_1)$ ,  $\log(\beta_1)$ ) for BMS-986277

Parameter	Means	Standard Deviations	Correlation
MAP component	(-1.065, 1.786)	(1.005, 0.697)	0.470
Weakly informative prior for BMS-986277 component	(-0.847, 0)	(1.53, 2)	0
Mixture Priors for BMS-986277	(-0.959, 0.884)	(1.005, 1.240)	0.055

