## 2 DOSE ESCALATION PROCESS AND SIMULATIONS IN MONOTHERAPY

### 2.1 Dose Escalation Process

Dose escalation recommendations for BMS-986277 monotherapy will be based on the inference from the Bayesian posterior and the probability that the true DLT rate for each dose lies in 1 of the following categories:

- [0%, 16%) under-dosing
- [16%, 33%) targeted toxicity
- [33%, 100%] excessive toxicity

Note: “[” or “[” is inclusive of the respective endpoint, and “(” or “)” exclusive of the respective endpoint.

These boundaries are similar to the toxicity boundaries used by a rule-based design (ie, 3 + 3 design) in that a minimum is set at 16% (~ 1 in 6) DLT rate and a maximum at 33% (~ 2 in 6) DLT

rate. Following the principle of EWOC, dose recommendations for the next cohort will be based on the Bayesian model after DLT information becomes available during the DLT period, accounting for all of the available data from the administered doses, and the candidate doses for the next cohort are the ones fulfilling the overdose criterion that there is no greater than 35% chance of excessive toxicity. Only the candidate doses will be considered for the next cohort. While the Bayesian model will use DLT information from the DLT period only, clinical assessment will take into consideration the totality of available data including PK/pharmacodynamics from all treated participants.

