## **2.2 Simulation Parameters**

Simulation study was done for monotherapy dose escalation using various hypothetical scenarios. One thousand trial simulations were used for each scenario. All simulations were run using EAST 6.3.1® software BLRM module for BMS-986277 monotherapy. The number of participants to be

treated in each cohort in a specific dose level, the stopping rules used to identify the BLRM-RD, and other simulation parameters are defined as:

- Fixed cohort size: 3
- Probability of overdosing:  $\leq 35\%$
- Target probability of toxicity: 0.33, the upper boundary of the targeted toxicity interval
- Probability of achieving the target toxicity:  $> 50\%$
- Maximum number of participants treated: 24
- Prior specification on model parameters:
  - Mean:  $\log(\alpha_1) = -0.959$ ,  $\log(\beta_1) = 0.884$
  - Variance:  $\log(\alpha_1) = 1.010$ ,  $\log(\beta_1) = 1.537$
  - Correlation: 0.055
- Posterior sampling method: Metropolis Hastings
- Minimum number of participants treated at a given dose level in order to identify the BLRM-RD: 6
- Maximum number of participants at a dose: 12

The provisional dose levels for BMS-986277 monotherapy are  $3 \times 10^{10}$ ,  $3 \times 10^{11}$ ,  $1 \times 10^{12}$ , and  $3 \times 10^{12}$  vp, with  $3 \times 10^{12}$  as the reference dose (dose expected to have 30% DLT).

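### Appendix 9's mixture-prior SDs (1.005, 1.240) cannot come from the components it describes (which give about 1.30, 1.74), and its worked outputs follow the narrower figures

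*Protocol*

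**What the plan says.** All references are to Protocol Appendix 9.

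- Section 1.2 builds the prior for (log alpha1, log beta1) from two bivariate normal components. One is a MAP component from enadenotucirev data. The other is a weakly informative component, included as "Reflecting the potential higher toxicity of BMS-986277 than enadenotucirev from activating T-cells and allowing for considerable prior uncertainty".
- Section 1.2.2 derives the weak component: the SD of log alpha1 "was set to 1.53 using the following steps", and the SD of log beta1 "was set to 2, which allows for considerably large prior uncertainty for the dose toxicity relationship".
- Section 1.2.3 gives half the weight to the MAP component, and "50% weight is assigned to the weakly informative component (described in Section 1.2.2"). Table 2 lists MAP means (-1.065, 1.786), SDs (1.005, 0.697), correlation 0.470; weak means (-0.847, 0), SDs (1.53, 2), correlation 0; and a mixture row with means (-0.959, 0.884), SDs (1.005, 1.240), correlation 0.055.
- Section 2.2, under "Prior specification on model parameters", loads that mixture row as a single set of moments: variances 1.010 and 1.537, correlation 0.055.
- Section 2.1 restricts escalation: the "candidate doses for the next cohort are the ones fulfilling the overdose criterion that there is no greater than 35% chance of excessive toxicity". If no planned dose qualifies, the model recommends stopping, and a lower dose may be sought.
- Section 3 illustrates the model after 0/3 DLTs at 3x10^10 and 1/3 at 3x10^11. The preferred dose, 1x10^12, has "the highest target dosing probability of 0.418", against 0.068 and 0.254 at the two lower doses. The overdose probability at 3x10^12 is 0.579.
- Section 3.1 ties the decision tree to the Section 1.2 prior ("With the current BMS-986277 prior specified in the Section 1.2 and all available DLT information") and tells the team it can use the tree to anticipate decisions.

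**The concern.** A mixture is at least as dispersed as the weighted average of its components. Here the mixture row is no wider than the MAP component for log alpha1, although half the weight sits on a component with a much larger SD. For log beta1 the mixture SD of 1.240 also looks too small beside a weak-component SD of 2.

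The weak component is there because BMS-986277 may be more toxic than its parent virus. If the loaded prior understates that uncertainty, the 35% overdose cap acts on a different posterior from the one the text describes. This matters most at the first-in-human starting dose, where little other data can correct the prior and the next planned step is 10-fold.

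**Working it through.** **Step 1. Moments of the described mixture** (weights 0.5 and 0.5, components from Table 2).

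Means: (-1.065 - 0.847)/2 = -0.956 and (1.786 + 0)/2 = 0.893. The printed -0.959 and 0.884 agree closely, so the 50/50 weighting is not the source of the problem.

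Variance = average component variance + (difference in means)^2/4.

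- log alpha1: 0.5 x 1.005^2 + 0.5 x 1.53^2 = 1.675; plus 0.218^2/4 = 0.012; total 1.687, SD 1.30.
- log beta1: 0.5 x 0.697^2 + 0.5 x 2^2 = 2.243; plus 1.786^2/4 = 0.797; total 3.040, SD 1.74.
- Covariance: 0.5 x 0.470 x 1.005 x 0.697 - 0.218 x 1.786/4 = 0.067; correlation 0.067/(1.299 x 1.744) = 0.03.

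The loaded variances, 1.010 and 1.537, lie below even the averages of the component variances, 1.675 and 2.243. No 50/50 mixture of these components can produce them.

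With weak-component SDs of 1 and 1 the same formulas give variances 0.505 + 0.5 + 0.012 = 1.017 (SD 1.008) and 0.243 + 0.5 + 0.797 = 1.540 (SD 1.241), and correlation 0.067/(1.008 x 1.241) = 0.054. The printed row is 1.005, 1.240, 0.055.

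**Step 2. Which prior produced the worked example?** Posteriors were computed on a grid for the two-parameter logistic model with reference dose 3x10^12. The described prior is taken two ways: as one normal with the correct mixture moments, and as the two-component mixture itself. Data: 0/3, then 1/3.

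| | Target, 3x10^10 | Target, 3x10^11 | Target, 1x10^12 | Overdose, 3x10^12 |
|---|---|---|---|---|
| Printed in Section 3 | 0.068 | 0.254 | 0.418 | 0.579 |
| Loaded prior | 0.068 | 0.257 | 0.415 | 0.56 |
| Described, single normal | 0.126 | 0.310 | 0.379 | 0.56 |
| Described, two-component | 0.177 | 0.334 | 0.355 | 0.53 |

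The three target probabilities identify the loaded prior. The fourth figure is missed by about 0.02 and does not separate the loaded prior from the single-normal form. The loaded prior also reproduces all four decisions that Section 3.1 states at 1x10^12.

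**Step 3. Recomputed decisions** (35% cap, highest target probability among qualifying doses, no skipping). Entries are overdose probabilities at the dose named.

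| Data | Dose | Loaded | Described, single normal | Described, two-component | Decision |
|---|---|---|---|---|---|
| 1/3 at 3x10^10 | 3x10^11 | 0.24 | 0.38 | 0.47 | escalate becomes stay |
| 2/3 at 3x10^10 | 3x10^10 | 0.34 | 0.58 | 0.71 | stay becomes stop |
| 0/3, then 2/3 at 3x10^11 | 3x10^11 | 0.24 | 0.37 | 0.46 | stay becomes de-escalate |
| 0/3, 0/3, then 2/3 at 1x10^12 | 1x10^12 | 0.24 | 0.34 | 0.40 | changes only in two-component form |

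In the first row the loaded prior moves up because the target probability is 0.39 at 3x10^11 against 0.245 at 3x10^10.

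**Step 4. How often the first decision would differ.** P(1 or 2 DLTs in 3) = 3p(1 - p). At p = 5% this is 0.14; at p = 16%, the highest starting-dose rate in Table 3, it is 0.40. The 1/3 outcome alone, 3p(1 - p)^2, contributes 0.135 and 0.34.

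**Step 5. Effect over a trial.** A simulation of 2,500 trials (cap on, no skipping, end-of-trial selection rule assumed) gave these results:

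- In the scenario with every dose on target, no dose was selected in 4.5% of trials under the loaded prior (Table 3 prints 5.1%), against 11.6% and 16.1% under the two described forms.
- With assumed true rates of 40/50/60/70%, an average of 3.8 participants were treated above the starting dose, against 2.0 and 1.8. No dose was selected in 55%, against 74% and 84%.

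**The case against.** Several points against a stronger reading stand.

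- **The tree itself was not read.** Figure 4 is not in the text available here, and no sentence states the 1/3 or 2/3 branch at 3x10^10. The decisions in Step 3 are recomputed and should be checked against the figure.
- **Section 3.1 is not false.** A reader might infer that it cites one prior and uses another. But the loaded row is itself part of Section 1.2.3, so the conflict lies inside Section 1.2, between the components and their own summary.
- **The narrower prior may have been intended.** If weak-component SDs of 1 and 1 were meant, the simulations may have run as planned; Section 1.2.2 and one row of Table 2 are then wrong. The documents do not say which was meant, so they do not support calling the loaded prior simply too narrow.
- **The loaded-prior stay after 2/3 is fragile.** It sits at 0.34 against 0.35, and these calculations miss a printed probability by about 0.02. Section 3.1 also says the model would choose 3x10^12 after 0/3 at the starting dose, whereas the overdose probability there comes out at 0.38 to 0.40. The sponsor's implementation may differ slightly. The 1/3 result has a much wider margin.
- **The Table 3 comparison is not like for like.** Those runs allowed dose skipping.
- **No cap is breached, and other safeguards exist.** Escalating at 0.24 satisfies the 35% rule. First participants are staggered by 7 days, skipping is barred, clinical assessment can hold a dose, and enadenotucirev showed no DLTs up to 6x10^12. At a true starting-dose rate of 5%, about 86% of first cohorts lead to the same decision.

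The arithmetic conflict in Table 2 survives all of these, as does the match between the worked example and the narrower row.

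**Conclusion.** The concern holds as an internal inconsistency with consequences for early dose decisions. The stated components imply SDs of about 1.30 and 1.74 and correlation 0.03; Table 2's mixture row and Section 2.2 use 1.005, 1.240 and 0.055. Since Section 2.2 lists the narrower values as simulation inputs and the Section 3 example follows them, Table 3 and the figures do not rest on the prior as described.

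The firm consequence is at 1/3 DLTs at the starting dose, where a 10-fold escalation becomes a stay in both forms of the described prior. After 2/3 the described prior clearly stops; what the loaded prior does there is too close to the cap to assert with confidence. Table 3 cannot show the difference for a toxic starting dose, because its highest rate there is 16%.

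These results assume the standard two-parameter logistic form, the 35% cap and the selection rule in Section 3. SAP Section 6.1 also mentions a 25% cap. At that level the loaded prior would still escalate after 1/3, only just (0.244), and would stop after 2/3.

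A reader might conclude that the protocol instructs unsafe escalation. The documents do not support that: the intended SDs are unknown and the model's output is not the only control. This should be fixed before the model guides dosing, but it does not invalidate the design.

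**What to change.** Decide which prior was intended, then make the text, table and inputs agree.

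1. **If 1.53 and 2 were intended:** correct the Table 2 mixture row to about SDs 1.30 and 1.74, correlation 0.03; load these values in Section 2.2; and re-run Table 3 and Figures 1 to 4. The price is more trials ending with no dose selected: about 12% to 16%, up from about 4.5%, in the scenario with every dose on target.
2. **If the narrower prior was intended:** change the weak-component SDs in Section 1.2.2 and Table 2 to 1 and 1, remove the derivation of 1.53, and justify the smaller uncertainty against the stated concern about T-cell activation.

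In either case add a simulation scenario with a toxic starting dose (for example 40%), and state in the text what the model recommends after 1/3 and 2/3 at 3x10^10.

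Two secondary checks: the Section 3.1 remark about 3x10^12 after 0/3, which changes no action because skipping is barred; and whether the Part 2 initial prior in Section 4.2.4, which lists the same means, also used these SDs.

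The work is one recalculation, a simulation re-run if option 1 applies, one added scenario and edits to Appendix 9. The planned maximum sample size, cap, target interval and stopping rules stay as they are.
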